5.2.1.2. New diagnosis of diabetes post-critical care (objective 1b)

Outcome defined as recording of the patient in the National Diabetes Audit database with a year of diagnosis in the calendar year after discharge .

Patients included in the model will be all those discharged alive from acute hospital following a critical care unit admission, excluding any with a pre-existing diagnosis of diabetes (as identified from data linkage with earlier years of data from the National Diabetes Audit, diagnostic coding within HES, or by recording of a primary or secondary reason for admission to the critical care unit associated with diabetes, e.g. diabetic ketoacidosis), those registered with a GP practice that did not submit data to the National Diabetes Audit in the subsequent year, and those in whom diabetes is diagnosed shortly after the episode of critical care

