The occurrence of hyperglycaemia is common among critically ill patients, regardless of diabetes status, and is associated with acute severity of illness and outcomes.^[6] Critical illness-related hyperglycaemia has previously been linked with subsequent development of Type 2 diabetes in small cohorts,^[7, 8] and data linkage between the CMP and the National Diabetes Audit will permit us to explore this in a much larger cohort and establish whether acute severity of hyperglycaemia or other risk factors are associated with the likelihood of developing Type 2 diabetes.

The occurrence of acute kidney injury (or acute renal failure) is common among critically ill patients and associated with high mortality,^[9] and has been strongly linked with subsequent end-stage renal disease.^[10] Data linkage between the CMP and the UK Renal Registry will enable us to evaluate this relationship in the UK and develop risk models to predict the requirement for long-term renal replacement among survivors of critical illness in the UK.

Survivors of critical care experience significant morbidity with substantial resultant healthcare resource use and costs. ^[11] Data linkage with Hospital Episode Statistics (HES) will enable us to estimate the cost of subsequent hospitalisations and its association with severity and/or duration of critical illness and other risk factors.

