5.2.1.3. New diagnosis of end-stage renal disease post-critical care (objective 1c)

Outcome defined as recording of the patient in the UK Renal Registry database with a date of diagnosis of end-stage renal disease within one year following the date of discharge from hospital.

Patients included in the model will be all those discharged alive from acute hospital following a critical care unit admission, excluding any with a pre-existing diagnosis of end-stage renal disease as identified from data linkage with earlier years of data from the UK Renal Registry or by recording of an ongoing requirement for renal replacement therapy for irreversible end-stage renal disease in the CMP database

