Date/time of 2222 call

Status at team arrival

Location of arrest

Presenting/first documented rhythm

Date/time resuscitation started

Date/time resuscitation stopped

Reason resuscitation stopped at end of team visit

Transient post-arrest location

Post-arrest location

Status at discharge from hospital

Sedated at discharge from hospital

CPC at discharge from hospital

Method used to assess CPC at discharge from hospital

Date of discharge from hospital

Date/time of death

UK Renal Registry

Common key

ERF patient flag

Date first seen by Renal Physician

Serum creatinine when first seen

Date of renal referral

Date of 1st eGFR of CKD5 (Date of Start of CKD5)

1st eGFR at start of CKD5

Date of 2nd eGFR 90 days later (CKD5)

2nd eGFR 90 days later (CKD5)

Date 1st ERF treatment

Primary disease code (ICD)

EDTA primary renal disease code

Date of last creatinine prior to start of ERF

Last creatinine prior to start of ERF

National Diabetes Audit

Common key

Diabetes Diagnosis Date

Diabetes Diagnosis Type Code

HbA1c (value and date)

National Adult	Cardiac	Surgery	Audit
----------------	---------	---------	-------

Common key

Angina status pre-surgery

Dyspnoea status pre-surgery

Number of previous MIs

Interval between surgery and last MI

Previous PCI

Previous cardiac surgery

Diabetes management

Cigarette smoking history

History of hypertension

Actual creatinine at time of surgery

Renal function/Dialysis

History of pulmonary disease

History of neurological disease

History of neurological dysfunction

Extracardiac arteriopathy

Pre-operative heart rhythm

Ejection fraction category

PA systolic

Intravenous nitrates or any heparin

Intravenous inotropes prior to anaesthesia

Ventilated (Pre-Operation)

Cardiogenic shock (Pre-Operation)

Date and time of operation

Operative urgency

Number of previous heart operations

CABG

Valve

Major aortic

Other Cardiac Procedures

Other Actual Cardiac Procedures

Total number of distal coronary anastomoses

Number of valves replaced/repaired

Native aortic valve pathology

Reason for repeat aortic valve operation

Aortic valve procedure

Native mitral valve pathology

Reason for repeat mitral valve operation

Mitral valve procedure

Native tricuspid valve pathology

Reason for repeat tricuspid valve operation

Tricuspid valve procedure

Native pulmonary valve pathology

Reason for repeat pulmonary valve operation

Pulmonary valve procedure

Number of aorta segments operated on

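### The diabetes outcome for objective 1b is tied to the calendar year after discharge, so its 12-month risk window opens anywhere from 0 to 12 months after discharge, and diagnoses in the discharge year cannot count

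*Protocol*

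**What the plan says.** Protocol section 5.2.1.2 defines the event by year, not by time since discharge: "Outcome defined as recording of the patient in the National Diabetes Audit database with a year of diagnosis in the calendar year after discharge". The population is patients discharged alive from acute hospital, with three kinds of exclusion:

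- known diabetes: "excluding any with a pre-existing diagnosis of diabetes";
- no audit return: "those registered with a GP practice that did not submit data to the National Diabetes Audit in the subsequent year";
- early diagnosis: "those in whom diabetes is diagnosed shortly after the episode of critical care". No number of days or months is given.

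The next section, 5.2.1.3, sets the renal outcome (objective 1c) differently, as a record "with a date of diagnosis of end-stage renal disease within one year following the date of discharge from hospital".

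Appendix 1 lists "Diabetes Diagnosis Date" and a diabetes type code among the National Diabetes Audit fields, and hospital discharge dates among the Case Mix Programme fields. Section 5.1.4 lists interval-censored, cause-specific and illness-death models in general terms, without assigning them to an objective. The background in section 1.1 says the linkage should show whether acute hyperglycaemia or other risk factors "are associated with the likelihood of developing Type 2 diabetes".

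**The concern.** A risk model predicts the chance of an event over a stated horizon. Under this definition the horizon depends on where in the calendar year the discharge falls. Two otherwise identical patients, one discharged in January and one in December, are followed over almost entirely different stretches of time after critical illness. The first must survive about 11 months before a diagnosis can count; the second must survive hardly any time. Section 1.1 itself notes that excess mortality continues for several years, so this difference in required survival is not trivial.

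The rule also leaves a gap. A patient discharged in January and diagnosed in September of the same year does not meet the outcome. Whether that patient is excluded or analysed as free of diabetes depends on how long *shortly after* lasts, which the protocol does not say. In either case, a patient removed for an early diagnosis is removed because of something that happened after discharge. Objective 4 intends immediate use of the models in practice, so the outcome needs a clear meaning.

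**Working it through.** **Stated figure.** The protocol gives no event count, capture rate or sample size for objective 1b, so there is nothing to reproduce. The window positions below follow from the definition alone. The shares of diagnoses rest on assumptions.

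**Could it simply mean 12 months from discharge?** Three features speak against that reading. The outcome uses a year of diagnosis, not a date. The practice-submission check refers to "those registered with a GP practice that did not submit data to the National Diabetes Audit in the subsequent year", which fits a whole later year. And section 5.2.1.3 uses plainly different words when a one-year window from discharge is meant.

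**Position of the window (no hazard assumption).** Let D be the fraction of the calendar year elapsed at discharge. The window opens 12(1 − D) months after discharge and closes at 12(2 − D) months. For mid-month discharges, D = (month − 0.5)/12.

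| Discharge | D | Window after discharge (months) | First-year diagnoses captured, constant hazard (= D) |
|---|---|---|---|
| mid-January | 0.042 | 11.5 to 23.5 | 4% |
| mid-June | 0.458 | 6.5 to 18.5 | 46% |
| mid-December | 0.958 | 0.5 to 12.5 | 96% |

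**Share of first-year diagnoses not counted.** Assume D is uniform on (0, 1). Section 3.2 fits the final models on the last two years of data, so each calendar month is covered equally; an even spread of discharges is still an assumption. Let T be the time to diagnosis in years, given T < 1. A first-year diagnosis falls in the discharge year if D + T < 1, so the share missed is E[1 − T].

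- Constant hazard, T uniform: 1 − 0.50 = 50%.
- Diagnoses rising linearly over the year, density 2t: 1 − 2/3 = 33%.
- Front-loaded, exponential decay at rate r per year truncated at one year, so that E[T] = 1/r − e^(−r)/(1 − e^(−r)): 58% for r = 1, 66% for r = 2, 77% for r = 4.

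**Excluded or scored as non-events?** Suppose *shortly after* means a fraction w of a year. Under constant hazard the excluded share is w, and the share scored as non-events is (1 − w)²/2. The lengths below are illustrative only.

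| Length | Excluded | Scored as non-events | Not counted in total |
|---|---|---|---|
| none | 0% | 50.0% | 50.0% |
| 30 days (w = 0.082) | 8.2% | 42.1% | 50.3% |
| 90 days (w = 0.247) | 24.7% | 28.4% | 53.0% |
| 180 days (w = 0.493) | 49.3% | 12.8% | 62.2% |

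If the phrase means the rest of the discharge year, all same-year diagnoses are excluded and none are misclassified.

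**Total events.** The window always lasts 12 months. Under constant hazard, ignoring death and early exclusion, the count equals that of a one-year window from discharge (ratio 1.00). The part of the window lying beyond day 365 is 1 − D of a year, with mean 0.50, so about half of the counted events are second-year diagnoses.

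**After the fix.** With a 365-day window from discharge, capture of first-year diagnoses is 100%. If an early exclusion of 30, 90 or 180 days were kept inside that window, capture would be 1 − w = 92%, 75% or 51%, the same for every discharge month.

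**The case against.** The strongest reply is that section 5.2.1.2 defines an outcome, not a model. Section 5.1.4 names logistic regression for mortality, return of circulation and hospital survival, not for diabetes. It separately lists methods for interval-censored onset in competition with death, and a diagnosis known only to the year is a natural reason for them. It also says that analysis plans will be finalised with the Clinical Advisory Groups. This stands to the extent that a reader might infer that patients who die remain in the analysis as non-events, and the protocol does not say so. It does not rescue the definition: no listed method can recover same-year diagnoses that the definition has already excluded or declared not to be events.

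Second, the choice may be deliberate. The early-diagnosis exclusion stands beside the exclusions for known diabetes and may be a washout of undiagnosed prior disease. If only the year of diagnosis is usable, the following calendar year is also the first that lies wholly after discharge. Appendix 1 names a date field but not its precision. Both reasons are fair, but neither requires a start that moves with discharge date or a washout of unstated length. A landmark analysis also sets early diagnoses aside; the difference is that it applies one rule to everyone and also requires survival to the landmark.

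Third, some stronger readings go beyond the document. A reader might infer that half of all diabetes events are lost, but the total is roughly unchanged. A reader might infer that the association between glucose and diabetes is diluted, but nothing in the protocol allows that to be sized. The absence of a Type 2 restriction is minor: the objective is worded as diabetes, and the requested type code lets the analysis plan settle it.

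**Conclusion.** The point holds. As written, the outcome has no common time horizon. The window opens from 0 to 12 months after discharge, and the survival needed to become at risk varies with it. This follows from the wording alone. Same-year diagnoses cannot be events, and their treatment as exclusions or non-events hangs on an undefined term. Exclusion for an early diagnosis selects on a post-discharge event.

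The share of first-year diagnoses not counted is about 50% if discharges are uniform over the year and the hazard is constant, and about 33% to 77% under the other hazard shapes tried with no early exclusion. These are illustrations under assumptions, not protocol figures. The effect is a shifted and uneven horizon with possible misclassification, not a halved event count. The definition should be corrected before the objective 1b model is fitted.

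**What to change.** Reword the outcome in section 5.2.1.2, using the requested diagnosis date and the hospital discharge date:

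- Count a diagnosis within a fixed 12-month window from hospital discharge, matching objective 1c, with death as a competing event.
- If a washout of undiagnosed prior diabetes is intended, state its length in advance, with the Clinical Advisory Group, as one landmark for all patients. Include only those alive and undiagnosed at the landmark, and count diagnoses in the 12 months after it. This replaces the open-ended early-diagnosis exclusion.
- If only the year of diagnosis is usable, keep same-year diagnoses as interval-censored events, with the interval running from discharge to year end, in the models already listed in section 5.1.4. A year alone cannot show that the diagnosis followed discharge, so the exclusion of known diabetes from the other sources must carry that part.

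The cost is one reworded definition and a check of the precision of the date field; Appendix 1 already lists the fields. The audit-submission check should be aligned with the new window, which may span two calendar years. With a landmark, diagnoses before it are reported separately. Restriction to Type 2 can be left to the analysis plan.

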5.2.1.3. New diagnosis of end-stage renal disease post-critical care (objective 1c)

Outcome defined as recording of the patient in the UK Renal Registry database with a date of diagnosis of end-stage renal disease within one year following the date of discharge from hospital.

Patients included in the model will be all those discharged alive from acute hospital following a critical care unit admission, excluding any with a pre-existing diagnosis of end-stage renal disease as identified from data linkage with earlier years of data from the UK Renal Registry or by recording of an ongoing requirement for renal replacement therapy for irreversible end-stage renal disease in the CMP database

5.2.1.4. Hospital resource use and costs post-critical care (objective 1d)

Outcome defined as number of days in acute hospital (LOS), either during the original hospital episode (as identified from CMP data) or subsequent hospital episodes (as identified through data linkage with HES). We assigned a cost to every patient recorded in CMP by using the Reference Cost reported by all English hospitals .

5.2.2. Risk models for cardiothoracic critical care (objective 2)

5.2.2.1. Mortality at discharge from acute hospital (objective 2a)

Outcome defined as mortality at discharge from acute hospital (acute hospital mortality), as used for the current risk model.

Patients included in the model will be all those admitted to a participating cardiothoracic critical care unit.

New risk factors, pre- and intra-operative risk factors obtained by data linkage with the National Adult Cardiac Surgery Audit (see Apendeix 1), will be assessed for their optimal functional form (see Appendix 2).

The starting point for the new risk model will be the previously developed risk model using CMP data only.

5.2.2.2. Mortality at 30-days, 90-days and 1-year (objective 2b)

Outcome defined as mortality at 30-days, 90-days and 1-year using the date of death obtained by data linkage with ONS.

Patients included in the model will be all those admitted to a participating cardiothoracic critical care unit.

The starting point for each new risk model will be the risk model developed in objective 2a.

5.2.2.3. Hospital resource use and costs post-critical care (objective 2c)

Outcome defined as number of days in acute hospital, either during the original hospital episode (as identified from CMP data) or subsequent hospital episodes (as identified through data linkage with HES).

Patients included in the risk prediction model will be all those discharged alive from the cardiothoracic critical care unit.

5.2.3. Risk models for in-hospital cardiac arrest (objective 3)

5.2.3.1. ROSC greater than 20 minutes and survival to hospital discharge (objective 3a)

Outcomes defined as ROSC greater than 20 minutes and survival to hospital discharge (hospital survival) from the existing NCAA data, the outcomes for the current risk models.

Patients included in the models will be all patients (aged 28 days or over) who received chest compressions and/or defibrillation following an in-hospital cardiac arrest and were attended by the hospital-based resuscitation team.

The starting point for the new risk models will be the previously developed risk models for each outcome.

New risk factors: pre-arrest risk factors obtained by data linkage with HES, the Charlson comorbidity index ^[28] and Elixhauser comorbidity measure ^[29] will be derived from International Classification of Disease (ICD-10) diagnostic codes and Office of Population Censuses and Surveys (OCPS) procedural codes, using methods employed recently by the UK Renal Registry ^[16], will be assessed for the optimal categorisation of the complex categorical risk factors.

5.2.3.2. Survival to 30 days, 90 days and 1 year and time to death (objective 3b)

Outcome defined as mortality at 30-days, 90-days and 1-year and days from cardiac arrest to death using the date of death obtained by data linkage with ONS.

Patients included in the models will be all patients (aged 28 days or over) who received chest compressions and/or defibrillation following an in-hospital cardiac arrest and were attended by the hospital-based resuscitation team.

The starting point for each new risk model will be the risk model for survival to hospital discharge developed in objective 3a.

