3.2. Sampling

The selection of sites is based on those participating in the CMP and NCAA.

The coverage of the CMP is extremely high, with 256 critical care units participating including over 97% of NHS adult general critical care units in England and Wales. We will link data for the period

1 April 2009 to 31 March 2015, enabling exploration of trends and fit of models over time, although only data from the last two years will be used to fit the final models as our previous research has established that the fit of risk models deteriorates over time. This will give a total sample size of over 850,000 admissions (700,000 critical care unit survivors) for exploring trends and fit over time with 330,000 admissions (280,000 critical care unit survivors) for model fitting. As the CMP is an ongoing programme, additional data will accrue while the development work is ongoing. At one year into the study, an additional 170,000 admissions (150,000 critical care unit survivors) will be available and the linkage will be updated providing data for external validation.

Of twenty-seven specialist cardiothoracic critical care units providing Level 3 (intensive) care, eight currently participate in the CMP. From 1 April 2009 to 31 March 2015 we will have a sample size of approximately 34,000 admissions to these units (3,000 deaths) for objective 2. The updated data linkage will include an additional 2,300 admissions (200 deaths) for external validation.

The coverage of NCAA is increasing and now stands at 181 hospitals, including over 75% of acute hospitals in England and Wales. From 1 April 2011 to 31 March 2015 we will have a sample size of approximately 56,000 in-hospital cardiac arrests (10,000 survivors) for objective 3. The updated data linkage will include an additional 16,000 in-hospital cardiac arrests (3,000 survivors) for external validation.

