Highest serum creatinine

Total urine output

Lowest haemoglobin

Highest haemoglobin

Lowest platelet count

Highest platelet count

Lowest white blood cell count

Associated neutrophil count (for lowest white blood cell count)

Highest white blood cell count

Associated neutrophil count (for highest white blood cell count)

Pupil reactivity (left eye)

Pupil reactivity (right eye)

Sedated or paralysed and sedated for whole of first 24 hours in the critical care unit

Neurological status

Lowest total Glasgow Coma Score (GCS)

Associated eye component (for lowest total GCS)

Associated motor component (for lowest total GCS)

Associated verbal component (for lowest total GCS)

Associated intubation status (for lowest total GCS)

Highest level of care received in the first 24 hours in the critical care unit

Number of basic respiratory support days

Number of advanced respiratory support days

Number of basic cardiovascular support days

Number of advanced cardiovascular support days

Number of renal support days

Number of neurological support days

Number of gastrointestinal support days

Number of dermatological support days

Number of liver support days

Number of Level 3 days

Number of Level 2 days

Number of Level 1 days

Number of Level 0 days

Treatment withheld/withdrawn

Status at discharge from the critical care unit

Date when fully ready to discharge

Time when fully ready to discharge

Reason for discharge from the critical care unit

Timeliness of discharge from the critical care unit

Date of discharge from the critical care unit

Time of discharge from the critical care unit

Level of care received at discharge from the critical care unit

Expected dependency post-acute hospital discharge

Brainstem death declared

Date of declaration of brainstem death

Time of declaration of brainstem death

Date of death

Time of death

Location (out)

Hospital housing location (out)

Date of ultimate discharge from ICU/HDU

Status at ultimate discharge from ICU/HDU

Date of discharge from hospital

Status at discharge from hospital

Destination post-discharge from hospital

Date of ultimate discharge from acute hospital

Status at ultimate discharge from acute hospital

Residence post-discharge from acute hospital

National Cardiac Arrest Audit

Common key

Unique hospital identifier (anonymous)

Age (whole years)

Sex

Ethnicity

Date of admission to/attendance at/visit to hospital

Reason for admission to/attendance at/visit to hospital

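### Objectives 2b and 3b (and 1a for ward deaths) take death only from the ONS link and do not say how an in-hospital death already recorded by the audit is classified when no ONS match exists

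*Protocol*

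**What the plan says.** **Outcome source.** Protocol 5.2.3.2 (objective 3b) covers mortality at 30 days, 90 days and 1 year and "days from cardiac arrest to death using the date of death obtained by data linkage with ONS". Section 5.2.2.2 (objective 2b) reads "Outcome defined as mortality at 30-days, 90-days and 1-year using the date of death obtained by data linkage with ONS". Section 5.2.1.1 (objective 1a) likewise names only linkage to ONS death registrations. None of the three gives a second source.

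**Populations.** For 2b, "Patients included in the model will be all those admitted to a participating cardiothoracic critical care unit". For 3b, "Patients included in the models will be all patients (aged 28 days or over) who received chest compressions and/or defibrillation" after an in-hospital arrest attended by the resuscitation team. Both therefore include patients who die before leaving hospital. Objective 1a is limited to patients who leave the unit alive, so only later deaths, including ward deaths, arise there.

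**What the audits hold.** Appendix 1 lists "Date/time of death" and hospital discharge status in the NCAA extract. The CMP extract has a date of death and "Status at ultimate discharge from acute hospital". Section 5.2.3.1 (objective 3a) takes hospital survival from NCAA itself.

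**Linkage.** The ONS fields listed in Appendix 1 are fact, date and causes of death. Appendix 2, step 1, promises to examine how complete and accurate the linkage is, within the step on candidate predictors and their missing data. Section 5.1.4 leaves the analysis plans to be finalised before modelling.

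**The concern.** Two parts of the same protocol can disagree about one patient. Someone recorded by NCAA as having died in hospital is a death in 3a. If the identifiers do not match an ONS registration, the same person has no death date in 3b, although the 3b model starts from the 3a model.

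The listed ONS fields contain no match status, so an absent death record looks the same for a true survivor and for a failed link. If absence is read as survival, patients with the risk profile of those who died enter the survivor group. That would tend to flatten coefficients, lower discrimination and understate mortality. The validation year comes from an update of the same linkage (5.1.2), so external validation would share the error and not expose it.

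Observed deaths also form the numerator of the standardised mortality ratio (5.1.1), and objective 4a carries the models into comparative reporting. If match failure differed between hospitals, the ratios would differ for reasons unrelated to care.

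The single source does not look like shorthand. Elsewhere the protocol combines sources: CMP or NCAA with HES for days in hospital, and registry with audit records for pre-existing diabetes and end-stage renal disease.

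**Working it through.** **Inputs from the protocol** (synopsis and 3.2)
- Objective 3: "approximately 56,000 in-hospital cardiac arrests (10,000 survivors) for objective 3"; validation 16,000 arrests, 3,000 survivors.
- Objective 2: 34,000 admissions, 31,000 unit survivors, 3,000 deaths; validation 2,300, 2,100 and 200.

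**Assumptions**
- The match-failure rate *f* is not given. A range of 1% to 10% is used, taken as equal in deaths and survivors.
- The 10,000 survivors are read as survivors to hospital discharge; section 3.2 does not say so.
- An unlinked patient counts as alive. This is one reading, and the protocol does not state it.

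**Step 1: reproduce the stated counts.** 34,000 − 31,000 = 3,000 and 2,300 − 2,100 = 200. Both match, so the objective 2 deaths are deaths in the unit; all hospital deaths would be somewhat more. For objective 3 no death count is stated. The implied counts are 56,000 − 10,000 = 46,000 and 16,000 − 3,000 = 13,000.

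**Step 2: effect if unlinked means alive.** With N patients, S survivors and D = N − S deaths:
- false survivors = D × *f*
- false share of apparent survivors = D*f* / (S + D*f*)
- apparent mortality = D(1 − *f*) / N

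| Data set | *f* | False survivors | Apparent survivors | False share | Apparent mortality |
|---|---|---|---|---|---|
| 3b development (true 82.1%) | 1% | 460 | 10,460 | 4.4% | 81.3% |
| | 2% | 920 | 10,920 | 8.4% | 80.5% |
| | 5% | 2,300 | 12,300 | 18.7% | 78.0% |
| | 10% | 4,600 | 14,600 | 31.5% | 73.9% |
| 3b validation (true 81.25%) | 5% | 650 | 3,650 | 17.8% | 77.2% |
| 2b development (true 8.8%) | 5% | 150 | 31,150 | 0.5% | 8.4% |
| | 10% | 300 | 31,300 | 1.0% | 7.9% |

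The contrast between 3b and 2b follows from the ratio of deaths to survivors: 46,000/10,000 = 4.6 against 3,000/31,000 ≈ 0.1.

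**Step 3: effect if unlinked patients are excluded.** Mortality is 46,000(1 − *f*) / 56,000(1 − *f*) = 82.1% at any *f*, so there is no bias if failure is unrelated to outcome. However, 46,000 × 0.05 = 2,300 known deaths would be dropped at 5%, and the population would no longer be all patients.

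**Step 4: effect of using audit deaths.** Misclassified in-hospital deaths fall to zero at any *f*. Deaths after discharge in unlinked patients remain. If 60% to 80% of the 10,000 survivors live to 1 year (assumption), 2,000 to 4,000 die after discharge. At *f* = 10%, 200 to 400 of these are missed. As a share of apparent 1-year survivors that is 200/8,200 = 2.4% to 400/6,400 = 6.3%. At *f* = 1% it is 20/8,020 ≈ 0.2% to 40/6,040 = 0.7%.

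**Step 5: illustration for hospital comparison.** Take two hospitals with identical true mortality and the same expected deaths, one with 10% and one with 2% match failure. The ratio of their standardised mortality ratios is 0.90/0.98 = 0.918, about 8% lower in the first. Nothing in the protocol says that failure varies in this way.

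**The case against.** A reader might infer that a known in-hospital death is scored as a 1-year survivor whenever the ONS link fails. The protocol contains no such rule. It names ONS as the source of the date and is silent on unlinked patients, who could be counted alive, excluded, set to missing or resolved from the audit record. That objection stands, and the figures in Step 2 are conditional for this reason.

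There are further points on the same side:
- **Linkage quality is not ignored.** The common key in 4.1 and the HES extract could flag patients with no HES match. Appendix 2 says linkage completeness will be explored. This helps only in part: a patient who matches HES but not the death registration would not be flagged, and the Appendix 2 step concerns predictors.
- **This may be analysis-plan detail.** A precedence rule between two death dates is commonly left to an analysis plan, and that plan is not shown. But the source of the outcome is not left open here; three sections fix it, and deferring the analysis plans does not change those definitions.
- **The size is assumed.** No failure rate is given, and none is said to differ by hospital. This stands.
- **The reach is limited.** Outcomes in 2a and 3a are discharge outcomes, with hospital survival in 3a taken from the audit, so they are not affected. For 2b the effect is small even on the adverse reading. Both points stand.

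**Conclusion.** The point holds as a defect in the outcome definition. Objectives 2b and 3b, and 1a for ward deaths after unit discharge, name ONS as the only source of death, although the audit extracts already record in-hospital deaths. No text says how an audit-recorded death without an ONS match is classified. The literal reading counts it as alive, and exclusion discards deaths that are known. The wording needs repair on either reading.

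It is potentially material for 3b. If unlinked means alive, assumed failure of 2% to 10% makes 8.4% to 31.5% of apparent survivors to discharge false and lowers apparent mortality by 1.6 to 8.2 percentage points. For 2b it is minor: 0.5% of apparent survivors at 5%, based on unit deaths only. For 1a no size can be given, because the protocol states no count of ward deaths.

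The 3b figures rest on the assumed failure rates, on reading survivors as survivors to hospital discharge, and on unlinked meaning alive. The documents do not support a claim that misclassification will occur, or that hospital comparisons will be distorted.

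**What to change.** In 5.2.1.1, 5.2.2.2 and 5.2.3.2, define death as the ONS-linked date or, where none is linked, the death date and status recorded in the CMP or NCAA. State which source prevails when the dates conflict. Rely on ONS alone only after the last discharge alive recorded by the audit. Report audit-recorded deaths without an ONS match by hospital, as a direct check on linkage quality in both the development and the validation data.

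The cost is a change of wording and a few lines of derivation code; every field needed is already in Appendix 1. A small number of date conflicts will need resolving. Deaths after discharge in unlinked patients would still be missed, and the report should say so. The change is best made before the linked outcomes are derived.
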